8. STATISTICAL ANALYSIS

8.1 General Data Handling Rules and Definitions

All data collected on CRFs will be provided in listings, except data collected only for confirmation of study entry criteria and for study administrative purposes. If any treated subject is found to be without valid documented informed consent, that subject's data will be excluded from the report, except as necessary to document the error.

All statistical analyses will be conducted using SAS version 9.4 or newer.

Except where specified, all continuous variables will be summarized with descriptive statistics (the number of non-missing values, mean, standard deviation, median, minimum and maximum) and all categorical variables will be summarized with frequency counts and percentages, by treatment and hepatic function group. Unless otherwise specified, the mean and median will be displayed to 1 more decimal place than the original data, and standard deviation will be displayed to two more decimal places than the original data. All frequencies will be rounded to 1 decimal place.

Missing data will be maintained as missing unless specified otherwise. For variables where missing data is imputed, the analysis dataset will contain one variable with the imputed value and the original variable with missing maintained as missing.

8.2 Subject Disposition

An overall disposition table for all subjects will be presented. This tabulation will include the number of subjects treated, completed, and those who withdraw study participation early. The number and percentage of subjects who are included in the PK, Safety and PD Populations will also be tabulated.

Subject disposition by site and hepatic function group will also be summarized for the Safety Population. These tabulations will include the number of subjects dosed, completed, and those who withdraw study participation early along with the corresponding primary reasons for early withdrawal.

Subjects in the Safety Population who prematurely discontinued from the study will be summarized by primary reason for early withdrawal.

Subject disposition will be listed for all subjects in the Safety Population.

8.3 Demographic and Baseline Characteristics

Demographic and baseline characteristics will be summarized by site and by hepatic function group for both the Safety and PK Populations and listed for the Safety Population.

Descriptive statistics (n, mean, median, standard deviation, minimum, and maximum) will be presented for continuous variables. Frequency distributions (counts and percentages) will be presented for categorical variables.

Medical history and baseline conditions will be summarized by hepatic function group and for all subjects and listed for the Safety Population. Physical examination, as well as prior and concomitant medications, will also be listed. Prior and concomitant medications will be listed with the drug names and ATC classification codes based on the data collected in the electronic CRF. The World Health Organization Drug Dictionary (WHO-DD), version March 2018 or newer, will be used to classify prior and concomitant medications by therapeutic class and drug name and hepatic impairment history.

Abnormalities in the subjects' medical and surgical histories will be coded using version 21.0 (or newer) of MedDRA Medical Dictionary for Regulatory Activities, and summarized and listed.

8.4 Safety Analyses

Safety analyses will be performed using the Safety Population, unless otherwise specified.

Safety measurements will include AEs, clinical laboratory tests (i.e. serum chemistry, hematology and urinalysis), ECGs, physical exams and vital signs. All safety data will be summarized by hepatic function group. Baseline values for clinical laboratory tests, vital signs and ECGs will be defined as the last evaluation performed prior to administration of study drug.

8.4.1 Adverse Events

All AEs will be coded to system organ class (SOC), and preferred term (PT), using the latest Medical Dictionary for Regulatory Activities coding dictionary (version to be specified in the clinical study report). All reported AEs will be listed, but only TEAEs will be summarized.

The incidence of all TEAEs will be summarized by hepatic function group. In the summary tables, subjects may be counted under multiple SOCs and PTs, but for each SOC and PT, subjects are only counted once. If a subject has the same AE on multiple occasions, the highest severity (severe > moderate > mild) or drug relationship (definite > probable > possible > not likely related > unrelated) recorded for the event will be presented. If severity is missing, subjects will be included as missing (for severity). If drug relationship is missing, subjects will be included in related tables (e.g., considered treatment related [TR]). Summary tables will be organized by SOC, then PT.

The following summaries will be presented for TEAEs for each hepatic function group and for all subjects for selective summaries for the Safety Population.

- Overall Summary of TEAEs by hepatic function group
- Incidence of TEAEs by hepatic function group, system organ class, and preferred term
- Incidence of Treatment Emergent Serious Adverse Events by hepatic function group, system organ class, and preferred term

Subjects who prematurely withdraw due to TEAEs and subjects with serious TEAEs will be listed for the Safety Population.

8.4.2 Laboratory Data

Summary tables for laboratory parameters (including hematology, chemistry, and urinalysis) will be summarized for subjects in the Safety Population. Summaries for change from baseline for hematology, chemistry, and urinalysis parameters will include descriptive statistics (the number of non-missing values, mean, standard deviation, median, minimum and maximum) for values and change from baseline values for all continuous variables, and frequency counts and percentages for categorical variables, by treatment. Subjects with laboratory data outside the normal range will be listed with abnormal values flagged.

8.4.3 Vital Signs (VS)

Summary tables for VS data will include descriptive statistics (the number of non-missing values, mean, standard deviation, median, minimum and maximum) for values and change from baseline values by hepatic function group.

A listing of VS results will be provided for all subjects in the Safety Population.

8.4.4 Electrocardiogram (ECG)

ECG parameters (RR interval, PR interval, QRS interval, QT interval, and QTcB interval) will be summarized by changes from baseline values by hepatic function group using descriptive statistics. For each parameter, only subjects who had both baseline and a post-baseline assessment will be included in the summary.

A listing of ECG results will be provided for all subjects in the Safety Population.

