ICH	International Council for Harmonisation
IEC	Independent Ethics Committee
IP	investigational product
INR	International Normalized Ratio
IRAE	immediately reportable adverse event

IRB	Institutional Review Board
IR	Immediate release
λ_z	terminal elimination phase rate constant
MedDRA	Medical Dictionary for Regulatory Activities
MDRD	modification of diet in renal disease study equation
NCA	non-compartmental analysis
nUGE	Normative UGE
OTC	over-the-counter
PD	pharmacodynamic
PE	physical examination
P-gp	p-glycoprotein
PK	pharmacokinetic
PR	The period that extends from the beginning of the P wave (the onset of atrial depolarization) until the beginning of the QRS complex (the onset of ventricular depolarization).
PT	preferred term
QRS	The combination of three of the graphical deflections seen on a typical electrocardiogram.
QT	Time from electrocardiogram Q wave to the end of the T wave corresponding to the electrical system
QTcB	QT corrected using Bazetts formula [QT/(RR ^{1/2})]
RR interval	intra-beat interval
SAE	serious adverse event
SAS	statistical analysis software
SD	standard deviation
SGLT1	sodium glucose cotransporter 1
SGLT2	sodium glucose cotransporter 2
SOC	system organ class
SOP	standard operating procedure
TEAE	treatment emergent adverse event
$t_{1/2}$	terminal elimination half life
t_{last}	time of last measurable concentration
T_{max}	time of maximum observed plasma concentration
T2DM	type 2 diabetes mellitus
UGE	urinary glucose excretion
ULN	upper limit of normal
UGT	uridine diphosphate glucuronosyltransferases
UTI	urinary tract infection
V_z/F	apparent volume of distribution
WHO-DD	World Health Organization Drug Dictionary

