3 INVESTIGATIONAL PLAN

3.1 Overall Study Design and Plan

Approximately 16 subjects (eight with moderate hepatic impairment [Child-Pugh total score 7-9] and eight healthy, matched controls) will be enrolled.

The Child-Pugh grading system will be used to assess the severity and prognosis of hepatic disease. Male or female subjects with hepatic impairment conforming to the Child-Pugh classification of B (Child-Pugh total score 7-9) based on the Child-Pugh scoring method described in [Appendix 2](#) will be enrolled. For each enrolled subject with liver dysfunction a matching control subject (healthy subject) with similar age (± 10 years), weight ($\pm 10\%$), sex, and smoking status will be enrolled.

Each subject will take a single bexagliflozin tablet, 20 mg, with 240 mL of water in the morning (approximately 8 a.m. to 10 a.m.) after an overnight fast. Food will be withheld for at least 2 h postdose. Water will be allowed as desired except for one hour before and after drug administration.

Blood samples for determining the plasma concentrations of bexagliflozin will be collected at predose and at 0.5, 1, 2, 3, 4, 5, 6, 8, 10, 12, 16, 24, 36, and 48 h postdose.

Urine samples for PD analysis will be collected predose and in the following intervals after dosing: 0–12, 12–24, 24–36, and 36–48 h.

Plasma concentrations of bexagliflozin will be determined by validated liquid chromatography-mass spectrometry (LC-MS/MS) methods.

The unbound fraction of bexagliflozin will be determined at 24 h postdose (or earlier if the 24 h postdose sample has a concentration below the limit of quantitation) and at the maximum plasma concentration for each subject by equilibrium dialysis.

Clinical laboratory tests and safety monitoring will be conducted during the treatment period and at the follow-up visit. The study event table is provided in [Appendix 1](#).

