4.3 Exclusion Criteria

Subjects who have any of the following attributes will be excluded from the study:

1. A clinically significant history of allergy to drugs or latex (at the investigator's discretion)
2. A positive alcohol or drug result based on urine sample or breathalyzer testing at screening or at clinic admission (D0). A subject may be eligible upon medical monitor

review and approval if the positive urine drug test is from stable dose of prescription medication

3. A record of donation of 400 mL of whole blood within two months, 200 mL of whole blood within one month, or blood components or plasma within 14 days prior to D0.
4. A history of exposure to an investigational drug within 30 days or 5 half-lives of the investigational drug prior to D0, whichever is longer
5. A history of exposure to any SGLT2 inhibitor within 3 months prior to D0 or participation in previous bexagliflozin clinical trials
6. A history of exposure to probenecid, rifampin or any potential strong UGT1A9 inducers or inhibitors within 2 months of D0
7. A clinically significantly abnormal screening ECG that includes but is not limited to: heart rate <40 or >110 bpm, QRS > 160 ms, QTc > 480 ms (corrected by Bazett's formula), or any clinically significant arrhythmia including Mobitz type II 2nd Degree Heartblock, and bifascicular block.
8. If destined for the hepatic impairment group, a seated systolic blood pressure <80 or > 160 , confirmed by repeat or diastolic blood pressure of < 40 or >100
9. If destined for the healthy control group, a seated systolic blood pressure <90 or > 140 , confirmed by repeat or diastolic blood pressure of < 40 or > 90
10. A history of HIV infection or a positive titer for human immunodeficiency virus (HIV) antibody
11. A history of vaccination (with the exception of the flu vaccine) within 30 days prior to D0
12. An estimated glomerular filtration rate (eGFR) < 60 mL min⁻¹ per 1.73 m² as calculated by the modification of diet in renal disease study equation (MDRD), at screening
13. Severe or moderate renal dysfunction or a history of kidney, other organ, bone marrow or stem cell transplant

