6.5 Electrocardiography

A 12-lead electrocardiography (ECG) will be conducted as listed in [Appendix 1](#) and whenever clinically indicated.

The data should be collected from the subject in the supine position after at least 5 minutes of rest. ECG parameters measured will be the RR interval, PR interval, QRS duration, and QT. Each ECG shall also be assessed by the investigator for signs of ischemia, clinically significant hypertrophy, and clinically significant T-wave abnormalities.

It is the investigator or designee's responsibility to review the results of the ECG as they become available. For each abnormal ECG result, the investigator shall ascertain if the abnormality represents a clinically significant change from the screening ECG for that individual subject. This determination, however, need not be made the first time an abnormal result is observed. The investigator may repeat the ECG to verify the results of the original

result. If the ECG result is determined to be a clinically significant and abnormal change from baseline for that subject, the finding shall be considered an AE.

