7.5 Day 1 (D1) Postdose

- Vital signs will be recorded at 4 h post-oral dose.
- A 12-lead ECG will be taken in the supine position after at least 5 min of rest at 4 h postdose.
- Urine samples for PD analysis will be collected at 0-12 h and 12-24 h after oral administration of bexagliflozin, as described in [Section 6.6.2.3](#).
- Blood samples for PK samples will be collected at 0.5, 1, 2, 3, 4, 5, 6, 8, 10, 12, 16 h after oral administration of bexagliflozin.

- Postdose concomitant medications and adverse event information will be collected as appropriate.

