6. SPECIFICATION OF ENDPOINTS AND VARIABLES

6.1 Demographic and Baseline Characteristics

Demographic variables consist of the following:

- Age in years (continuous) derived as the integer value of $(\text{informed consent date} - \text{date of birth} + 1)/365.25$
- Sex
- Race
- Ethnicity

Baseline characteristics consist of the following:

- Body mass index (BMI) (kg m^{-2})
- Weight (kg)

- Smoking status (non-smoker, current smoker, former smoker)
- Height (cm)
- Vital signs (VS)
 - systolic blood pressure (SBP, mmHg)
 - diastolic blood pressure (DBP, mmHg)
 - oral cavity temperature (°C)
 - pulse (beats per minute)
 - respiration rate (breaths/min)
- Electrocardiogram (ECG) parameters
 - RR interval (msec)
 - PR interval (msec)
 - QRS duration/interval (msec)
 - QT interval (msec)
 - QTcB interval (msec) (corrected by Bazett’s formula)
- Medical history and baseline conditions
- Clinical laboratory test values
- Prior and concomitant medication
- Physical examination (PE)

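### Bazett is the only QT correction in the SAP, so a within-subject heart-rate change between the fasted predose ECG and the 4-h ECG can mimic or mask a QTc change; adding QTcF costs almost nothing

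*SAP*

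**What the plan says.** **Correction used.** SAP 8.4.4: "ECG parameters (RR interval, PR interval, QRS interval, QT interval, and QTcB interval) will be summarized by changes from baseline values by hepatic function group". SAP 6.1 lists QTcB among the baseline ECG variables, and SAP 6.3.6 names it again. The protocol's abbreviation list defines the term as "QT corrected using Bazetts formula", that is QT/RR^(1/2), and exclusion criterion 7 in Protocol 4.3 uses the same correction. No other correction appears in either document.

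**What is recorded.** Protocol 6.5: "ECG parameters measured will be the RR interval, PR interval, QRS duration, and QT". QTc is thus a derived quantity, and both ingredients of any alternative correction are collected.

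**Baseline.** SAP 6.3.6 takes the last ECG before dosing. By the schedule this is the Day 1 predose ECG, when subjects have fasted overnight for at least 10 h (Protocol 5.3).

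**Postdose ECGs.** Protocol 7.5: "A 12-lead ECG will be taken in the supine position after at least 5 min of rest at 4 h postdose". The others are at 48 h and Day 15 (Protocol Appendix 1).

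**Food.** Protocol 3.1: "Food will be withheld for at least 2 h postdose". No later meal time is fixed.

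**Other summaries.** Pulse change from baseline is summarised by hepatic function group (SAP 6.3.5 and 8.4.3). ECG and vital-sign results are listed by subject.

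**The concern.** Bazett's formula removes the effect of heart rate fully only if QT varies with the square root of RR. If the true dependence is weaker, QTcB rises whenever the rate rises, with no change in repolarisation, and falls when the rate falls.

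The comparison that matters most is exposed to this. The Protocol Introduction puts peak concentration at 3 to 5 h and the half-life at 7.8 to 9.7 h. By 48 h, about 5 to 6 half-lives have passed (48/9.7 = 4.9; 48/7.8 = 6.2), so the 4-h ECG is the only scheduled one near peak exposure. It is compared with a fasted reading and may be taken after food. The Introduction also describes a diuretic effect with mild volume depletion. Every subject is dosed and no drug-free ECG is taken at a matching clock time, so nothing separates a drug effect from a meal or time-of-day effect on rate.

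At stake is the reading of one descriptive safety table. A rate shift might be taken for QTc prolongation, or a fall in rate might conceal some.

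**Working it through.** The documents state no QTc effect size, so there is no planned figure to reproduce. The check is how far each correction moves when only the heart rate changes.

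**Inputs from the documents**
- QTcB = QT/RR^(1/2), with RR = 60/HR in seconds (protocol abbreviation list).
- QT and RR are recorded at every ECG (Protocol 6.5).

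**Assumptions, not in the documents**
- With no drug effect, QT = Q60 × RR^k, where Q60 is the QT at 60 bpm.
- Q60 = 420 ms, varied from 400 to 450 ms; k = 0.25, 1/3, 0.40 or 0.50.
- Heart rate rises from 60 to 70 bpm. This is an illustration; the documents give no expected change.

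**Comparator.** QTcF = QT/RR^(1/3) (Fridericia).

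**Formulas.** At 60 bpm RR = 1 and both corrected values equal Q60. At a new rate:
- change in QTcB = Q60 × (RR^(k − 1/2) − 1)
- change in QTcF = Q60 × (RR^(k − 1/3) − 1)

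**One case in full, k = 1/3.** RR = 60/70 = 0.85714. QT = 420 × 0.85714^(1/3) = 398.96 ms. QTcB = 398.96/0.92582 = 430.9 ms, a change of +10.9 ms. QTcF = 398.96/0.94991 = 420.0 ms, a change of 0.

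**All four exponents (Q60 = 420 ms, 60 to 70 bpm)**

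| k | QT at 70 bpm (ms) | Change in QTcB (ms) | Change in QTcF (ms) |
|---|---|---|---|
| 0.25 | 404.1 | +16.5 | +5.4 |
| 1/3 | 399.0 | +10.9 | 0 |
| 0.40 | 394.9 | +6.5 | −4.3 |
| 0.50 | 388.8 | 0 | −10.7 |

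**Sensitivity**
- For Q60 from 400 to 450 ms, the QTcB change is 15.7 to 17.7 ms at k = 0.25, 10.4 to 11.7 at 1/3, 6.2 to 7.0 at 0.40, and 0 at 0.50.
- At k = 1/3 and Q60 = 420 ms, other rises give +5.6 ms (60 to 65 bpm), +15.9 ms (60 to 75) and +9.7 ms (70 to 80).
- A fall from 70 to 60 bpm reverses every sign in the table. At k = 1/3, QTcB would drop by 10.9 ms and could mask a real prolongation of that size.

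**What the table shows.** The zero for QTcF at k = 1/3 holds by construction, because that exponent is the Fridericia formula itself. QTcF has the smaller error for k below about 5/12 = 0.42, midway between 1/3 and 1/2, and QTcB has the smaller error above it. For k between 1/3 and 1/2, a rate rise makes QTcB too high and QTcF too low, so the two together bracket the true change.

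**Can the planned summaries supply this?** Both corrections are nonlinear in RR and apply to each subject separately. Group means of QT and RR allow at best an approximation to the mean QTcF change, and they do not give its spread or its extreme values.

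**The case against.** The strongest reply is that the plan already guards against a misreading. The sentence that reports QTcB also reports changes in RR and uncorrected QT by group, and pulse is measured at 4 h and summarised. A reader would see a rate shift in the adjacent rows. ECGs are listed by subject, so QTcF could be worked out at reporting. ECG is one descriptive item under the secondary safety objective. The SAP plans no hypothesis test and no on-study QTc threshold.

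Most of this stands and limits the weight of the point. Seeing that the rate moved does not, however, show how much of the QTcB change it explains. Working out QTcF from listings after the data are known is weaker than naming it in advance.

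Four stronger readings are tempting, and the documents do not support them.
- **The entry range sets the size of the artefact.** Exclusion criterion 7 bars only "heart rate <40 or >110 bpm", but that limit applies at screening and describes spread between subjects. Change from baseline depends on each subject's own rate change, whose size is not given.
- **The hepatic impairment group would show a spurious effect relative to controls.** Both groups have the same fasting rule, dose and ECG times, so a common meal effect would largely cancel between groups. No differential rate shift is shown.
- **A meal does come before the 4-h ECG.** It may; the protocol gives only a minimum fasting time after dosing.
- **QTcF is right and QTcB wrong.** That depends on an exponent the documents do not give. At k = 0.50 QTcF errs by −10.7 ms, in the direction that hides prolongation.

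**Conclusion.** The point holds as a low-cost improvement. With Bazett alone, a within-subject rate change between the fasted baseline and the 4-h ECG can pass for a QTc change or conceal one. For a 10 bpm rise from 60 bpm with a QT of 420 ms, the artefact in QTcB is 0 to +16.5 ms over exponents 0.50 to 0.25. For QTcF it runs from −10.7 to +5.4 ms, and it is smaller in size than that of QTcB at three of the four exponents tried.

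These figures rest on the assumed power law, the assumed baseline QT and an illustrative rate change. They show what can happen, not what is expected. No bias between the groups is demonstrated, and the primary PK/PD analysis is not affected.

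**What to change.** - **SAP 6.1 and 6.3.6:** add QTcF = QT/RR^(1/3), with RR in seconds, derived per subject and per ECG from the recorded QT and RR.
- **SAP 8.4.4:** summarise QTcF change from baseline by hepatic function group and time point, beside QTcB and the RR change already planned. State that any QTc change will be interpreted from both corrections together with the rate change, without treating either correction as decisive.
- **Eligibility:** leave exclusion criterion 7 as it is.

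The cost is one derived variable and a few rows in an existing table. It needs no new ECGs, no further data and no protocol amendment. SAP section 10 already provides for a revision before database lock.

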8.4.5 Physical examinations (PE)

Physical examination results will be presented in individual subject data listings.

8.4.6 Pregnancy Test

Pregnancy test results prior to treatment will be listed.

8.4.7 Protocol Deviations

All protocol deviations will be listed.

9. ANALYSES PERFORMED BEFORE DATABASE CLOSURE

No interim analyses are planned for this study.

10. CHANGES FROM METHODS PLANNED IN THE PROTOCOL

Any changes to methods planned in this SAP will be documented in a revision to this statistical plan prior to database lock, or identified in the clinical study report.

11. STATISTICAL SOFTWARE

The statistical software to be used for generation of the tables, listings, and figures is SAS[®] version 9.4.

